Appendix T. Class VI and Class VII Topical Corticosteroid Examples

Class	Generic Name or Local Equivalent	%
VI	Prednicarbate	0.05
	Triamcinolone acetonide	0.025
	Desonide	0.05
	Fluocinolone acetonide	0.01
	Triamcinolone acetonide	0.025
	Flumethasone pivalate	0.03
	Fluocinolone acetonide	0.01
	Desonide	0.05
	Triamcinolone acetonide	0.025
	Betamethasone valerate	0.01
VII	Betamethasone valerate	0.2
	Hydrocortisone acetate	1.0
	Hydrocortisone	1.0, 2.5
	Methylprednisolone	0.25
	Fluorometholone	0.025
	Hydrocortisone	1.0, 2.5

Risankizumab/ABBV-066
M16-244 Protocol Amendment 1
EudraCT 2016-003113-94

Appendix U. Follow-up Phone Call

Site Name/Number: _____ / _____

Subject Number: _____

Contact subjects that signed the protocol Amendment 1 ICF approximately 140 days (20 weeks) following last study drug administration.

Date of Call/Visit: _____

- Lost to Follow-up (check this box if subject was not willing to provide any follow-up information or you were unable to speak to the subject following at least two phone call attempts and one certified letter).
- No Events Reported

At the Follow-up Phone Call:

- Record any adverse events (AEs) and/or serious adverse events (SAEs) that occurred since the subject's last study visit. Document all AEs/SAEs in source records and EDC system. Report all SAEs to AbbVie within 24 hours of awareness of the event.
- Request update to the status of any AE that was ongoing at the last study visit.
- Request update to any concomitant medication(s) that was ongoing at the last study visit. Record any change in concomitant medication in source documents and EDC.

Name of person completing form (printed): _____

Risankizumab/ABBV-066
M16-244 Protocol Amendment 1
EudraCT 2016-003113-94

Signature of person completing form: _____

Date: _____

Please email this completed form to [REDACTED]

Appendix V. Protocol Amendment: List of Changes

The summary of changes is listed in Section [1.1](#).

Specific Protocol Changes

Section 1.0 Title Page

"Sponsor Contact:" previously read:

Sponsor Contact:

Has been changed to read:

Sponsor Contact:

Section 1.0 Title Page

"Emergency Medical Contact;" "Bldg" previously read:

[name]

Has been changed to read:

[name]

Section 1.1 Synopsis**Subsection Diagnosis and Main Criteria for Inclusion/Exclusion:****Heading "Main Inclusion:"****Criterion 2 previously read:**

Women of childbearing potential who are sexually active, must agree to use at least one accepted method of contraception throughout the study, including 16 weeks after last dose of study drug is given.

Has been changed to read:

Women of childbearing potential who are sexually active, must agree to use at least one accepted method of contraception throughout the study, including 20 weeks after last dose of study drug is given.

Section 1.1 Synopsis**Subsection Diagnosis and Main Criteria for Inclusion/Exclusion:****Heading "Main Exclusion:"****Criterion 1 previously read:**

Female subject who is pregnant, breastfeeding or is considering becoming pregnant during study participation, including 16 weeks after the last dose of study drug is given.

Has been changed to read:

Female subject who is pregnant, breastfeeding or is considering becoming pregnant during study participation, including 20 weeks after the last dose of study drug is given.

Section 1.2 List of Abbreviations and Definition of Terms**Subsection Abbreviations****Add:**

$t_{1/2}$ Half-life

Section 3.3 Differences Statement**First sentence previously read:**

Study M16-244 is a 52 week multicenter, single-arm, open-label extension (OLE), consisting of 36 weeks of study drug administration and 16 weeks follow-up, to Study 1311.5.

Has been changed to read:

[figure not shown]
[figure not shown]
Study M16-244 is a 52 week multicenter, single-arm, open-label extension (OLE), consisting of 36 weeks of study drug administration and 20 weeks follow-up, to Study 1311.5.

Section 5.1 Overall Study Design and Plan: Description**Subsection Follow-Up Period****First paragraph previously read:**

Subjects will have follow-up visits at Week 48 and 52. All Follow-Up Visit procedures are noted in Appendix C. Subjects who discontinue study drug treatment early will need to attend an early End of Treatment (EOT) visit ideally within 2 weeks after the decision and preferably prior to the administration of any new therapies. An additional End of Study (EOS) visit, 16 weeks after their last dose of study drug, is required to determine the status of any ongoing AEs/SAEs or the occurrence of any new AEs/SAEs (see Appendix C and Section 5.4.1).

Has been changed to read:

Subjects will have follow-up visits at Week 48 and 52 and a Follow-up Phone call 20 weeks after the last dose of study drug. All Follow-up Visit procedures are noted in [Appendix C](#). Subjects who discontinue study drug treatment early will need to attend an early End of Treatment (EOT) visit ideally within 2 weeks after the decision and preferably prior to the administration of any new therapies. An End of Study (EOS) visit 16 weeks after the last dose of study drug and a Follow-up Phone Call 20 weeks after the last dose of study drug is required to determine the status of any ongoing AEs/SAEs or the occurrence of any new AEs/SAEs (see [Appendix C](#) and Section [5.4.1](#)).

Figure 2. Study M16-244 Study Design**Previously read:****Has been changed to read:****Section 5.2.1 Inclusion Criteria****Criterion 2 previously read:**

Women of childbearing potential must agree to use at least one of the following methods of contraception throughout the study including 16 weeks after the last study drug dose is given.

Has been changed to read:

Women of childbearing potential must agree to use at least one of the following methods of contraception throughout the study including 20 weeks after the last study drug dose is given.

Section 5.2.2 Exclusion Criteria**Criterion 1 previously read:**

Female subject who is pregnant, breastfeeding or is considering becoming pregnant during study participation, including 16 weeks after the last dose of study drug is given.

Has been changed to read:

Female subject who is pregnant, breastfeeding or is considering becoming pregnant during study participation, including 20 weeks after the last dose of study drug is given.

Section 5.2.4 Contraception Recommendations and Pregnancy**First paragraph, last sentence previously read:**

The method chosen must be practiced throughout the study including 16 weeks after the last dose of study drug is given.

Has been changed to read:

The method chosen must be practiced throughout the study including 20 weeks after the last dose of study drug is given.

Section 5.4.1 Discontinuation of Individual Subjects**First bullet previously read:**

A subject does not attain a protocol defined (defined as an improvement in tender and swollen joint count of $\geq 20\%$ compared with the baseline in Study 1311.5) at 2 consecutive visits at Week 12 visit, or thereafter.

Has been changed to read:

A subject does not attain a protocol defined response (defined as an improvement in tender and swollen joint count of $\geq 20\%$ compared with the baseline in Study 1311.5) at 2 consecutive visits at Week 12 visit, or thereafter.

Section 5.4.1 Discontinuation of Individual Subjects**Third paragraph, last sentence previously read:**

For subjects that prematurely discontinue, study drug will not be given at the early EOT visit and subjects should attend their EOS Visit 16 weeks after last study drug dose to determine the status of any ongoing AEs/SAEs or the occurrence of any new AEs/SAEs (see Appendix C).

Has been changed to read:

[figure not shown]
[figure not shown]
For subjects that prematurely discontinue, study drug will not be given at the early EOT visit and subjects should attend their EOS Visit 16 weeks after last study drug dose and complete a Follow-up Phone Call 20 weeks after the last dose of study drug to determine the status of any ongoing AEs/SAEs or the occurrence of any new AEs/SAEs (see Appendix C).

Section 6.1.4 Adverse Event Collection Period**First paragraph, first sentence previously read:**

All adverse events reported from the time of study drug administration until 16 weeks, following discontinuation of study drug administration have elapsed will be collected, whether solicited or spontaneously reported by the subject.

Has been changed to read:

All adverse events reported from the time of study drug administration until 20 weeks, following discontinuation of study drug administration have elapsed will be collected, whether solicited or spontaneously reported by the subject.

Figure 3. Adverse Event Collection**Previously read:****Has been changed to read:****Section 6.1.5 Adverse Event Reporting****"Primary Therapeutic Area Medical Director:," "Bldg" previously read:**

[name]

Has been changed to read:

[name]

Section 7.0 Protocol Deviations

"Alternate Contact:" previously read:

Has been changed to read:

**Section 8.1.6.2.1 Treatment-Emergent Adverse Events**

First paragraph, last sentence previously read:

AEs starting more than 105 days following the last dose of study drug will not be included in summaries of TEAEs

Has been changed to read:

AEs starting more than 140 days following the last dose of study drug will not be included in summaries of TEAEs.

Section 13.0 Completion of the Study**Fourth paragraph previously read:**

The end-of-study is defined as the date of the last subject's last visit, 16 weeks after the final dose of study drug, see Appendix C.

Has been changed to read:

The EOS is defined as the date of the last subject's last scheduled visit or the date of the Follow-up Phone Call, whichever is later, see [Appendix C](#).

Appendix C. Study Activities
Previously read:

	Treatment				Follow-Up		EOS (EOT/Early EOT + 16 Weeks)
	V1	V2	V3	V4	V5 (EOT/Early EOT ^s)	V6	
Week	0^a	4^t	12	24	36	48	52
Day	1	29 ± 4	85 ± 4	169 ± 4	253 ± 4	336 ± 4	365 ± 4
Informed Consent ^b	X						
Inclusion/exclusion criteria	X						
Medical/Surgical History ^c	X ^a						
Patient's Global Assessment of Disease Activity (VAS) (PtGA) ^d	X ^a	X	X	X	X	X	X
Patient's Assessment of PsA Pain Intensity (VAS) ^d	X ^a	X	X	X	X	X	X
HAQ-DI ^d	X ^a	X	X	X	X	X	X
BASDAI ^{d,m}	X ^a						
SF-36v2 ^d	X ^a	X	X	X	X	X	X
FACIT-F ^d	X ^a						
Vital Signs ^e	X ^a	X	X	X	X	X	X
ECG ^e	X ^a						
Physical Exam ^e (c = complete, t = targeted)	X-c ^a	X-t	X-t	X-t	X-t	X-t	X-c

Week	Treatment					Follow-Up	
	V1	V2	V3	V4	V5 (EOT/Early EOT ^s)	V6	EOS (EOT/Early EOT + 16 Weeks)
0 ^a	4 ^t	12	24	36	48	52	
1	29 ± 4	85 ± 4	169 ± 4	253 ± 4	336 ± 4	365 ± 4	
Concomitant Therapy ^f	X ^a	X	X	X	X	X	X
Adverse Event Assessment ^g	X ^a	X	X	X	X	X	X
Tender Joint Count (TJC 68) ^h	X ^a	X	X	X	X	X	X
Swollen Joint Count (SJC 66) ^h	X ^a	X	X	X	X	X	X
PASI ^{h,u}	X ^a	X	X	X	X	X	X
BSA ^h	X ^a	X	X	X	X	X	X
Static Physician's Global Assessment for Psoriasis (sPGA) ^{h,u}	X ^a	X	X	X	X	X	X
Physician's Global Assessment of Disease Activity (PhGA) (VAS) ^h	X ^a	X	X	X	X	X	X
Leeds Dactylitis Index (LDI) ^h	X ^a	X	X	X	X	X	X
Leeds Enthesitis Index (LEI) ^h	X ^a	X	X	X	X	X	X
SPARCC ^h	X ^a	X	X	X	X	X	X
mNAPSI ^h	X ^a	X	X	X	X	X	X
mTSS (X-ray) ^j							
Pregnancy Test ^j	X ^a	X	X	X	X	X	X

Week	Treatment					Follow-Up	
	V1	V2	V3	V4	V5 (EOT/Early EOT ^s)	V6	EOS (EOT/Early EOT + 16 Weeks)
0 ^a	4 ^t	12	24	36	48	52	
1	29 ± 4	85 ± 4	169 ± 4	253 ± 4	336 ± 4	365 ± 4	
Safety Labs (Chemistry, Hematology, Urinalysis) ^{k,v}	X ^a	X	X	X	X	X	X
hsCRP for DAS ^k	X ^a	X	X	X	X	X	X
Blood Sample for PK ^{k,l}	X ^a	X	X	X	X	X	X
Blood Sample for ADA Assay ^{k,l}	X ^a	X	X	X	X	X	X
TB screening ^{k,n}			X			X ^r	
Local tolerability ^o	X	X	X	X	X		
Study drug administration	X	X ^p (additional)	X	X	X		
Monitoring for hypersensitivity reaction ^q	X	X	X	X			
Conclusion of Subject participation						X	

Has been changed to read:

	Treatment				Follow-Up		Follow-up Phone Call
	V1	V2	V3	V4	V5 (EOT/Early EOT ^s)	V6	
Week	0 ^a	4 ^t	12	24	36	48	56
Day	1	29 ± 4	85 ± 4	169 ± 4	253 ± 4	336 ± 4	365 ± 4
Informed Consent ^b	X						392 ± 4
Inclusion/exclusion criteria	X						
Medical/Surgical History ^c	X ^a						
Patient's Global Assessment of Disease Activity (VAS) (PtGA) ^d	X ^a	X	X	X	X	X	
Patient's Assessment of PsA Pain Intensity (VAS) ^d	X ^a	X	X	X	X	X	
HAQ-DI ^d	X ^a	X	X	X	X	X	
BASDAI ^{d,m}	X ^a				X	X	X
SF-36v2 ^d	X ^a	X	X	X	X	X	X
FACIT-F ^d	X ^a				X	X	
Vital Signs ^e	X ^a	X	X	X	X	X	X
ECG ^e	X ^a				X	X	X
Physical Exam ^e (c = complete, t = targeted)	X-c ^a	X-t	X-t	X-t	X-t	X-t	X-c
Concomitant Therapy ^f	X ^a	X	X	X	X	X	X

	Treatment					Follow-Up	
	V1	V2	V3	V4	V5 (EOT/Early EOT ^s)	V6	EOS (EOT/Early EOT + 16 Weeks)
Week	0^a	4^t	12	24	36	48	52
Day	1	29 ± 4	85 ± 4	169 ± 4	253 ± 4	336 ± 4	365 ± 4
Adverse Event Assessment ^g	X ^a	X	X	X	X	X	X
Tender Joint Count (TJC 68) ^h	X ^a	X	X	X	X	X	X
Swollen Joint Count (SJC 66) ^h	X ^a	X	X	X	X	X	X
PASI ^{h,u}	X ^a	X	X	X	X	X	X
BSA ^h	X ^a	X	X	X	X	X	X
Static Physician's Global Assessment for Psoriasis (sPGA) ^{h,u}	X ^a	X	X	X	X	X	X
Physician's Global Assessment of Disease Activity (PhGA) (VAS) ^h	X ^a	X	X	X	X	X	X
Leeds Dactylitis Index (LDI) ^h	X ^a	X	X	X	X	X	X
Leeds Enthesitis Index (LEI) ^h	X ^a	X	X	X	X	X	X
SPARCC ^h	X ^a	X	X	X	X	X	X
mNAPSI ^h	X ^a	X	X	X	X	X	X
mTSS (X-ray) ⁱ				X	X	X	X
Pregnancy Test ^j	X ^a	X	X	X	X	X	X
Safety Labs (Chemistry, Hematology, Urinalysis) ^{k,v}	X ^a	X	X	X	X	X	X

		Treatment				Follow-Up			
		V1	V2	V3	V4	V5 (EOT/Early EOT ^s)	V6	EOS (EOT/Early EOT + 16 Weeks)	Follow-up Phone Call
Week	0^a	4^t	12	24	36	48	52	56	
Day	1	29 ± 4	85 ± 4	169 ± 4	253 ± 4	336 ± 4	365 ± 4	392 ± 4	
hsCRP for DAS ^k	X ^a	X	X	X	X	X	X	X	
Blood Sample for PK ^{k,l}	X ^a	X	X	X	X	X	X	X	
Blood Sample for ADA Assay ^{k,l}	X ^a	X	X	X	X	X	X	X	
TB screening ^{k,n}					X		X ^r		
Local tolerability ^o	X	X	X	X	X	X			
Study drug administration	X	X ^p (additional)	X	X	X				
Monitoring for hypersensitivity reaction ^q	X	X	X	X	X				
Conclusion of Subject participation							X		

Appendix D. Local Requirements**Subsection Local Requirements – Japan****Heading "Section 7.0: Protocol Deviations"**

"Alternate Contact:" previously read:

Has been changed to read:

Appendix D. Local Requirements
Subsection Local Requirements – Japan
Heading "Appendix C: Study Activities Table"
Table previously read:

	Treatment					Follow-Up	
	V1	V2	V3	V4	V5 (EOT/Early EOT)	V6	EOS (EOT/Early EOT + 16 Weeks)
Week	0	4	12	24	36	48	52
Day	1 ± 4	29 ± 4	85 ± 4	169 ± 4	253 ± 4	336 ± 4	365 ± 4
HBV DNA*	X			X			X

Has been changed to read:

	Treatment					Follow-Up		Follow-up Phone Call
	V1	V2	V3	V4	V5 (EOT/Early EOT)	V6	EOS (EOT/Early EOT + 16 Weeks)	
Week	0	4	12	24	36	48	52	56
Day	1 ± 4	29 ± 4	85 ± 4	169 ± 4	253 ± 4	336 ± 4	365 ± 4	365 ± 4
HBV DNA*	X			X			X	

### **3.0                   Introduction**

This statistical analysis plan (SAP) describes the statistical analyses to be completed by the Data and Statistical Science Department for ABBV-066 Study M16-244. It provides details to further elaborate statistical methods as outlined in the protocol and describes analysis conventions to guide the statistical programming work.

Unless noted otherwise, all analyses will be performed using SAS version 9.4 (SAS Institute Inc., Cary, NC 27513) under the UNIX operating system.

### **4.0                   Study Objectives, Design and Procedures**

#### **4.1                   Primary Objectives**

The primary objective of Study M16-244 is to assess the safety and tolerability of risankizumab in PsA subjects who have completed all doses of study drug and the Week 24 visit in Study 1311.5.

#### **4.2                   Secondary Objectives**

The secondary objectives include the assessment of symptomatic and structural efficacy of risankizumab in PsA subjects who completed all doses of study drug and the Week 24 visit in Study 1311.5.

#### **4.3                   Overall Study Design and Plan**

This is a 52-week multicenter, single-arm, OLE study to assess safety, tolerability and efficacy of risankizumab in PsA subjects who have completed all doses of study drug and the Week 24 visit of Study 1311.5 (Phase 2 randomized clinical trial in PsA subjects, sponsored by Boehringer Ingelheim).

Subjects who complete all doses of study drug and the Week 24 visit in Study 1311.5, meet all inclusion criteria (Section 5.2.1 of the protocol) and none of the exclusion criteria (Section 5.2.2 of the protocol) have the option to sign the informed consent form and enter

the OLE study, receiving risankizumab 150 mg administered every 12 weeks with an additional dose of risankizumab made available at the Week 4 of the OLE study visit for those subjects that have not achieved a protocol defined response (defined as an improvement in tender and swollen joint count of  $\geq 20\%$  compared with the baseline in Study 1311.5), provided the investigator believes this may be beneficial to the subject.

[figure not shown]
If the Study M16-244 Week 0 visit occurs on the same day or in the 4 days following the Study 1311.5 Week 24 visit, only selected activities are required as some activities are common to both studies and are not required twice. See Study Activity Table in Appendix C of the protocol. If the OLE Week 0 visit occurs  $> 4$  days and  $\leq 8$  weeks after the Study 1311.5 Week 24 visit, all procedures specified in Appendix C of the protocol at Week 0 of the OLE study are required.

Subjects that enroll in the OLE study are no longer enrolled in Study 1311.5 and will not complete the Week 28 or Week 32 visits in Study 1311.5.

Subjects who are not enrolled in Study M16-244 within 8 weeks of the Study 1311.5 Week 24 visit are not eligible to participate in Study M16-244.

This study is anticipated to enroll up to 180 subjects. Study visits will occur at Week 0/Enrollment, Week 4, 12, 24, 36, 48 and 52. A  $\pm 4$  day window is permitted around scheduled study visits after enrollment.

A schematic of the study design is shown below in [Figure 1](#).

**Figure 1. Study M16-244 Study Design**

#### 4.4 Sample Size

Study 1311.5 will enroll approximately 180 subjects. The sample size of Study M16-244 will depend on how many subjects completed all doses of study medication and the Week 24 visit of Study 1311.5 and enroll in this OLE.

#### 4.5 Interim Analysis

No interim efficacy analysis is planned for this study.

#### 4.6 Data Monitoring Committee

An independent DMC operating under a charter is responsible for reviewing safety data periodically to ensure subject safety and to monitor the conduct of the trial and the integrity of the data. An independent analytic team external to both BI and AbbVie will provide the unblinded results to the DMC.

## 5.0 Analysis Sets

### 5.1 Definition for Analysis Sets

#### Safety Analysis Set

The Safety Analysis Set consists of all subjects who have received at least one dose of study medication in Study M16-244. All efficacy and safety analyses will be based on the Safety Analysis Set.

All efficacy and safety analyses will be summarized for "All ABBV-066 150 mg q12wks with optional wk4 dose" group, which includes all subjects who received at least one dose of ABBV-066 150 mg every 12 weeks in Study M16-244 (with an optional additional dose at Week 4 for subjects with < 20% improvement in tender joint count (TJC) or swollen joint count (SJC)), regardless of what treatment group they were randomized to in Study 1311.5.

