5.2 Selection of Study Population

5.2.1 Inclusion Criteria

1. Subjects who have completed all doses of study drug and Week 24 visit of Study 1311.5.
2. Women of childbearing potential must agree to use at least one of the following methods of contraception throughout the study including 20 weeks after the last study drug dose is given.
 - combined (estrogen and progestogen containing) hormonal birth control (oral, intravaginal, transdermal) associated with inhibition of ovulation initiated at least 1 month prior to study participation.
 - progestogen-only hormonal birth control (oral, injectable, implantable) associated with inhibition of ovulation initiated at least 1 month prior to study participation.
 - bilateral tubal occlusion/ligation
 - intrauterine device (IUD)
 - intrauterine hormone-releasing system (IUS).
 - Vasectomized sexual partner(s) (the vasectomized partner(s) should have received medical assessment of the surgical success and is the sole sexual partner of the trial participant).

- True abstinence: Refraining from heterosexual intercourse when this is in line with the preferred and usual lifestyle of the subject (periodic abstinence [e.g., calendar, ovulation, symptothermal, post-ovulation methods] and withdrawal are not acceptable).

Women of childbearing potential are defined as having experienced menarche and are:

- not postmenopausal (12 months with no menses without an alternative medical cause) and are
- not permanently sterilized (e.g., hysterectomy, bilateral oophorectomy or bilateral salpingectomy).

3. Women of childbearing potential must have a negative urine pregnancy test at Baseline (Week 0/V1).
4. Subjects must voluntarily sign and date an informed consent, approved by an Independent Ethics Committee (IEC)/Institutional Review Board (IRB), prior to the initiation of any study specific procedures.
5. Subject is judged to be in good health as determined by the Investigator.

See [Appendix D](#) for inclusion criterion specific to France.

Rationale for the Inclusion Criteria:

- 1, 5 To select the adequate subject population
- 2, 3 The impact of risankizumab on pregnancy and reproduction is unknown
- 4 In accordance with harmonized Good Clinical Practice (GCP)

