5.6.4 Selection of Doses in the Study

Risankizumab doses of 150 mg subcutaneous administered with different dosing frequencies (every 4 weeks to every 12 weeks) and 75 mg subcutaneous administered as a single dose are currently being evaluated in the Phase 2 study (Study 1311.5) in subjects with psoriatic arthritis. In addition, risankizumab dose of 150 mg subcutaneous administered at Week 0, 4 and then every 12 weeks for up to 104 weeks is currently being evaluated in the Phase 3 studies in subjects with psoriasis. The Phase 2 studies of risankizumab in subjects with psoriasis and CD have evaluated risankizumab doses up to 180 mg subcutaneous administered at Week 0, 4 and then every 12 weeks (in subjects with psoriasis) and up to 600 mg administered intravenously every 4 weeks for up to 26 weeks as induction treatment followed by 180 mg subcutaneous administered every 8 weeks during maintenance period (in subjects with CD).

As of March 2016, 546 adult subjects have received at least 1 dose of risankizumab in all completed and ongoing studies. Unblinded safety data (at least up to completion of randomized treatment period) are available on 465 subjects with PsO, CD and ankylosing spondylitis subjects, 358 of whom received risankizumab.

The doses of risankizumab evaluated in these studies have been found to be well tolerated. There was no relationship between risankizumab dose and the overall frequency of AEs, the occurrence of AEs in specific organ classes, or any individual AE (Risankizumab IB, version 7).

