### **PsA Medical History and Disease Characteristics at Baseline**

- Categorical:
  - MDA (Minimal Disease Activity) for PsA
  - sPGA (Static Physician Global Assessment) assessed in subjects with ≥ 3% BSA of psoriatic plaques
  - Presence of Dactylitis (yes/no)
  - Presence of Enthesitis based on LEI (yes/no)
  - Presence of Enthesitis based on SPARCC (yes/no)
  - Presence of nail psoriasis (yes/no)
  - Body Surface Area (BSA) of psoriatic plaques: ≥ 3% vs < 3%
  - Prior exposure to TNF antagonists (TNFi's; Experienced versus Naive)
  - Concurrent exposure to Methotrexate (Concurrent use versus Non-concurrent use)
  - Presence of inflammatory spondylitis (yes/no)
  - Duration of PsA Categories (≤ 5, [5, 10], > 10)
  - Rheumatoid Factor (RF) status: Positive (≥ 15) or Negative (< 15)
- Continuous
  - PASI (Psoriasis Area and Severity Index) assessed in subjects with ≥ 3% BSA of psoriatic plaques
  - DAS28 (Disease Activity Score in 28 joints) – hsCRP
  - Dactylitis count in subjects with dactylitis at baseline 0 – 20
  - Leeds Dactylitis Index (LDI) in subjects with dactylitis at baseline
  - Leeds Enthesitis Index (LEI) in subjects with enthesitis (based on LEI) at baseline (yes/no) 0 – 6
  - Duration since diagnosis of PsA in years

- CASPAR classification criteria total score
- SPARCC (Spondyloarthritis Research Consortium of Canada) Enthesitis Index in subjects with enthesitis (based on SPARCC) at baseline (yes/no) 0 – 16
- mNAPSI (Modified Nail Psoriasis Severity Index) assessed in subjects with nail psoriasis at baseline 0 – 130

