### 10.4 Further Efficacy Analyses

Further efficacy endpoints will include, but are not limited to, the following:

- ACR 50 response at all measured time points in Study M16-244
- ACR 70 at all measured time points in Study M16-244
- Change in Tender Joint Count at all measured time points in Study M16-244 as compared to baseline in Study 1311.5
- Change in Swollen Joint Count at all measured time points in Study M16-244 as compared to baseline in Study 1311.5
- Change in HAQ-DI at all measured time points in Study M16-244 as compared to baseline in Study 1311.5

- Change in SF-36 at all measured time points in Study M16-244 as compared to baseline in Study 1311.5
- Change in Dactylitis count at all measured time points in Study M16-244 as compared to baseline in Study 1311.5 in subjects with dactylitis at baseline
- Change in SPARCC Enthesitis Index at all measured time points in Study M16-244 as compared to baseline in Study 1311.5 in subjects with enthesitis based on SPARCC sites at baseline
- Change in mNAPSI at all measured time points in Study M16-244 as compared to baseline in Study 1311.5
- Change in PhGA (VAS) at all measured time points in Study M16-244 as compared to baseline in Study 1311.5
- Change in Patient's Assessment of PsA Pain Intensity (VAS) at all measured time points in Study M16-244 as compared to baseline in Study 1311.5
- Change in PtGA assessments at all measured time points in Study M16-244 as compared to baseline in Study 1311.5
- Change in High sensitivity C-Reactive Protein (hsCRP) at all measured time points in Study M16-244 as compared to baseline in Study 1311.5.
- Minimal disease activity (MDA) at all measured time points in Study M16-244
- Change in DAS28-hsCRP at all measured time points in Study M16-244 as compared to baseline in Study 1311.5
- PsO endpoints assessed at all measured time points in Study M16-244 in subjects with a  $\geq 3\%$  baseline PsO BSA in Study 1311.5:
  - PASI 75 and PASI 90 response
  - Change in sPGA clear and almost clear
- EULAR (European League Against Rheumatism) response at all measured time points in Study M16-244
- Change in PsARC (Psoriatic Arthritis Response Criteria) at all measured time points in Study M16-244 as compared to baseline in Study 1311.5
- Presence of dactylitis (yes/no) at all measured time points in Study M16-244 in subjects with dactylitis at baseline

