- Change in LDI at all measured time points in Study M16-244 as compared to baseline in Study 1311.5 in subjects with dactylitis at baseline
- Change in LEI at all measured time points in Study M16-244 as compared to baseline in Study 1311.5 in subjects with enthesitis based on LEI sites at baseline
- Change in FACIT-FATIGUE at all measured time points in Study M16-244 as compared to baseline in Study 1311.5
- Change in BASDAI at all measured time points in Study M16-244 (in subjects with baseline inflammatory spondylitis, based on investigator judgment, in Study 1311.5) as compared to baseline in Study 1311.5

Further efficacy endpoints will be summarized descriptively. Continuous endpoints will be summarized with the use of box plots, while proportions will be displayed by histograms as appropriate.

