## **10.6 Efficacy Subgroup Analysis**

A subgroup analyses based on prior randomization and weight will be performed to evaluate the consistency of efficacy in the secondary endpoints.

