### **11.3 Analysis of Laboratory Data**

Changes from Baseline in Study 1311.5 in continuous laboratory parameters will be summarized by n, mean, standard deviation, minimum value, median, and maximum value for the group of subjects that received Placebo in Study 1311.5 and for the group of subjects that received Risankizumab in Study 1311.5.

Shift tables from Baseline to the final value (the last assessment during each treatment period) according to the normal range will be provided for each hematology, clinical chemistry parameter and urinalysis parameter. The laboratory data will be categorized as low, normal, or high based on the normal ranges of the laboratory used in this study. The shift tables will tabulate the number and percentage of subjects with Baseline in Study 1311.5 values below/within/above the normal range versus final values below/within/above the normal range.

Frequencies and percentages of subjects with post Baseline lab values meeting the following criteria in [Table 15](#) and [Table 16](#) will be summarized.

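### Most further efficacy endpoints are shown only for one pool of prior-placebo and prior-risankizumab subjects, so visit estimates match no single duration of risankizumab exposure; mNAPSI change is also not limited to baseline nail disease

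*SAP*

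**What the plan says.** SAP 5.1 defines one reporting group for efficacy and safety: everyone dosed in Study M16-244, "regardless of what treatment group they were randomized to in Study 1311.5". The only efficacy breakdown by earlier treatment is in SAP 10.6: "A subgroup analyses based on prior randomization and weight will be performed to evaluate the consistency of efficacy in the secondary endpoints". SAP 10.3 lists those endpoints as ACR20, mTSS, HAQ-DI and SF-36. For the list in SAP 10.4 the plan says "Further efficacy endpoints will be summarized descriptively" and gives no split. HAQ-DI and SF-36 appear in both lists, so 10.6 covers them.

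Other parts of the SAP do separate prior treatment. Section 11.2.1 tabulates treatment-emergent events by SOC and PT, and serious events and events leading to discontinuation, by prior as well as current treatment. Section 11.3 summarises laboratory changes "for the group of subjects that received Placebo in Study 1311.5 and for the group of subjects that received Risankizumab in Study 1311.5".

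On nail disease, the endpoint in SAP 10.4 is "Change in mNAPSI at all measured time points in Study M16-244 as compared to baseline in Study 1311.5", with no restriction on who contributes. The baseline table in SAP 7.1 describes mNAPSI as "assessed in subjects with nail psoriasis at baseline". In the same 10.4 list, dactylitis count and presence, LDI, LEI and SPARCC are limited to subjects affected at baseline.

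**The concern.** A by-visit table in an extension study is usually read as a course of response on drug. Here one column holds two courses. Prior-placebo subjects are starting risankizumab and the others have already had some, yet both are measured from the same Study 1311.5 baseline. The level at an early visit then depends partly on how many subjects came from placebo. A rise across visits can reflect onset in new starters, further gain in the rest, or both, and the table cannot tell these apart. At Week 0 the prior-placebo subjects have had no risankizumab, although the column carries the risankizumab label. Summaries are of observed cases (SAP 6.5) and persistent non-responders are withdrawn (Protocol 5.4.1), so the mix of prior arms may also change between visits without the reader seeing it.

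The mNAPSI question is separate. A subject who starts at 0 cannot improve. If such subjects enter the change analysis, the mean change is pulled toward zero, and it rests on different subjects from the baseline mean printed in the same report.

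**Working it through.** The plan gives no power or precision figure to reproduce; the study is descriptive.

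**1. Time since first risankizumab dose.**
- Entry follows 24 weeks in the earlier trial: "Subjects who have completed all doses of study drug and Week 24 visit of Study 1311.5" (Protocol 5.2.1).
- The gap before OLE entry is 0 to 8 weeks (Protocol 5.1 and 5.2.2).
- I take active subjects to have had their first risankizumab dose at Study 1311.5 Week 0, and placebo subjects to have had theirs in the OLE. SAP 11.2.1 supports the latter: it counts prior-placebo subjects' events toward risankizumab after the first Study M16-244 dose.
- At OLE week k, prior placebo = k and prior risankizumab = 24 + gap + k. The difference is 24 to 32 weeks at every visit.

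| OLE week | Prior placebo | Prior risankizumab |
|---|---|---|
| 0 | 0 | 24–32 |
| 4 | 4 | 28–36 |
| 12 | 12 | 36–44 |
| 24 | 24 | 48–56 |
| 36 | 36 | 60–68 |
| 48 | 48 | 72–80 |
| 52 | 52 | 76–84 |

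**2. Which endpoints are affected early.** SAP Table 1 has a Week 4 window for joint counts, pain, global assessments, PASI, sPGA and hsCRP, and hence for ACR50/70 and DAS28. In Table 4 the first post-dose window for LDI, LEI, SPARCC and mNAPSI is Week 12. In Tables 2 and 3 it is Week 24 for BASDAI and FACIT-Fatigue, so the Week 4 contrast does not apply to those.

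**3. Effect on a pooled rate.** Let w be the prior-placebo share and d the true gap in response between the two groups. The pooled rate lies w × d below the prior-risankizumab rate and (1 − w) × d above the prior-placebo rate. Neither w nor d is in the documents. Assuming w = 0.10 to 0.33 and d = 0.10 to 0.30:
- below prior risankizumab: from 0.10 × 0.10 = 1 point to 0.33 × 0.30 = 9.9 points;
- above prior placebo: from 0.67 × 0.10 = 6.7 points to 0.90 × 0.30 = 27 points.

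**4. Precision if split.** Enrolment is at most 180; I assume 120 to 180. The prior-placebo column then holds 0.10 × 120 = 12 to 0.33 × 180 ≈ 59 subjects. At a response near 30%, the exact 95% interval (the method in SAP 10.1) is 9.9% to 65.1% for 4/12 and 19.2% to 43.9% for 18/59.

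**5. mNAPSI.** Let q be the share with nail disease among subjects who have a recorded baseline. If unaffected subjects do not change, the overall mean change is q times the change in affected subjects. Assuming q = 0.5 to 0.9 and a change of −12 in affected subjects, the table would show −6.0 to −10.8. If unaffected subjects worsen, it moves further toward zero.

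I follow SAP 6.1 and 10.4 in taking the Study 1311.5 baseline. SAP Table 8 heads the other continuous endpoints with a Study M16-244 baseline, which should be reconciled.

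**The case against.** **Main measures are covered.** ACR20 by prior randomization will show the contrast between onset and maintenance, and what remains is secondary in rank and untested. That limits the importance of the point. But in a descriptive study the displays are the result, and ACR20 does not speak for skin, enthesitis or MDA.

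**PASI may already be split.** SAP 10.7.9 summarises PASI by treatment group, and SAP 8.0 refers to each treatment group as if there were several. The wording is loose, but SAP 7.1 ties the analysis treatment group to section 5.1, which has only one. Where the SAP means both periods, it names prior and current treatment explicitly. This leaves at most an ambiguity.

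**Two columns do not give a clean exposure.** This stands. Study 1311.5 regimens were 150 mg "administered with different dosing frequencies (every 4 weeks to every 12 weeks) and 75 mg subcutaneous administered as a single dose", so a prior-risankizumab column still mixes exposures, and some of its subjects had one dose long before OLE entry. The prior-placebo column may also be small.

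**mNAPSI dilution is not shown.** This also stands in part. If Study 1311.5 recorded baseline mNAPSI only in affected subjects, the observed-case rule already limits the change analysis to them. The unrestricted wording also matches Protocol 5.3.3.3.

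A reader might infer that all results outside the secondary endpoints are pooled. They are not: adverse events and laboratory changes are separated by prior treatment. Nor are the visit estimates without meaning, since they describe time since OLE entry.

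**Conclusion.** The point holds for the further efficacy endpoints of SAP 10.4 other than HAQ-DI and SF-36. Their pooled estimates combine subjects 24 to 32 weeks apart in time since first risankizumab dose. That interval follows from the documents, given first active dosing at Study 1311.5 Week 0. The effect is largest at Weeks 0 to 12 for endpoints measured then. It is probably smaller by Weeks 48–52, when all remaining subjects are at least 48 weeks from first dose.

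The size in response points cannot be determined. The ranges above rest on assumed placebo shares and response gaps, and a claim of a large distortion would have no support in the documents. No hypothesis test is affected.

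For mNAPSI, the inconsistency between 7.1 and 10.4 is plain. Dilution occurs only if subjects without nail disease have a recorded Study 1311.5 baseline of 0.

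**What to change.** Extend SAP 10.6 so that the prior-randomization presentation covers the 10.4 endpoints as well. Give a prior-placebo column, a prior-risankizumab column and the pool as total, with randomized arms shown where numbers allow because the earlier regimens differ. Reword 5.1 so that it agrees with this and with the splits already in 11.2.1 and 11.3, and state which groups are meant wherever the SAP says treatment group.

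Separately, define the mNAPSI change population as subjects with nail psoriasis at the Study 1311.5 baseline, in line with 7.1 and the other domains in 10.4.

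No new data are needed, since the prior arm is known. The cost is more table columns, one population flag, and wide intervals in the prior-placebo column, which should be presented as description only.
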